4.5.6 Laboratory, Biomarker, and Other Biological Samples

Samples for the following laboratory tests will be sent to the study site's local laboratory for analysis:

- Hematology: WBC count, RBC count, hemoglobin, hematocrit, platelet count, and differential count (neutrophils, eosinophils, basophils, monocytes, lymphocytes, other cells)
- Chemistry panel (serum or plasma): bicarbonate or total carbon dioxide (if considered standard of care for the region), sodium, potassium, chloride, glucose, BUN or urea, creatinine, total protein, albumin, phosphate, calcium, total bilirubin, ALP, ALT, AST, and LDH
- Coagulation: INR, and aPTT
- Thyroid function testing: thyroid-stimulating hormone, free T3 (or total T3 for sites where free T3 is not performed), and free T4
- HIV serology
- HBV serology: HBsAg, HBsAb, and total HBcAb for all participants; HBV DNA for participants with negative HBsAg and HBsAb tests and a positive total HBcAb test
- HCV serology: HCV antibody for all participants; HCV RNA for participants with a positive HCV antibody test
- Pregnancy test

All women of childbearing potential will have a serum pregnancy test performed at screening. Urine (or serum, if urine is not feasible) pregnancy tests will be performed at specified subsequent visits. If a urine pregnancy test is positive, it must be confirmed by a serum pregnancy test.

A woman is considered to be of childbearing potential if she is postmenarchal, has not reached a postmenopausal state (≥ 12 continuous months of amenorrhea with no identified cause other than menopause), and is not permanently infertile due to surgery (i.e., removal of ovaries, fallopian tubes,

and/or uterus) or another cause as determined by the investigator (e.g., Müllerian agenesis).

- Urinalysis (pH, specific gravity, glucose, protein, ketones, and blood); dipstick permitted

The following samples will be sent to one or several central laboratories or to the Sponsor or a designee for analysis:

- Serum samples for atezolizumab PK analysis through use of a validated assay
- Serum samples for assessment of ADAs to atezolizumab through use of a validated assay
- Archival or newly collected tumor tissue sample obtained at baseline for determination of PD-L1 expression and EGFR and/or ALK, if central testing is required

For PD-L1 expression, a representative FFPE tumor specimen in a paraffin block (preferred) or at least 5 slides containing unstained, freshly cut, serial sections must be submitted along with an associated pathology report prior to study enrollment.

Tumor tissue should be of good quality as determined on the basis of total and viable tumor content. Samples must contain viable tumor cells that preserve cellular context and tissue architecture regardless of needle gauge or retrieval method. Samples collected via resection, core-needle biopsy (at least three cores, embedded in a single paraffin block), or excisional, incisional, punch, or forceps biopsy are acceptable. Fine-needle aspiration (defined as samples that do not preserve tissue architecture and yield cell suspension and/or smears), brushing, cell pellets from pleural effusion, and lavage samples are not acceptable. Tumor tissue from bone metastases that have been decalcified is not acceptable.

If archival tumor tissue is unavailable or is determined to be unsuitable for required testing, tumor tissue must be obtained from a biopsy performed at prescreening/screening. A biopsy may also be performed at prescreening/screening if a participant's archival tissue test results do not meet eligibility criteria (see Section 4.1) or does not meet the required quality criteria explained above.

For participants who may harbor EGFR and/or ALK mutations and their status is unknown or not assessed with a Health Authority approved test (i.e., adhering to local drug/device regulations) and performed per manufacturer's recommendations and requirements, these must be assessed at a central laboratory (see Section 4.1.2.1 for exclusion criteria). If samples are submitted for central testing, additional unstained slides must be provided (see additional details in the laboratory manual) along with an associated pathology report prior to study enrollment.

For sampling procedures, storage conditions, and shipment instructions, see the laboratory manual.

Biological samples will be destroyed no later than the time of completion of the final Clinical Study Report, with the following exceptions:

- Serum samples collected for PK or immunogenicity analysis may be needed for additional immunogenicity characterization and for PK or immunogenicity assay development and validation; therefore, these samples will be destroyed no later than 5 years after the final Clinical Study Report has been completed.
- Tumor tissue samples collected for screening will be destroyed no later than 5 years after the final Clinical Study Report has been completed.
- For enrolled participants, remaining archival tissue blocks will be returned to the site upon request or no later than the time of completion of the Clinical Study Report, whichever occurs first. For individuals who are not enrolled, remaining archival tissue blocks will be returned to the site no later than 6 weeks after eligibility determination.

When a participant withdraws from the study, samples collected prior to the date of withdrawal may still be analyzed, unless the participant specifically requests that the samples be destroyed or local laws require destruction of the samples. However, if samples have been tested prior to withdrawal, results from those tests will remain as part of the overall research data.

Data arising from sample analysis will be subject to the confidentiality standards described in Section 8.4.

4.5.7 Electrocardiograms

An electrocardiogram (ECG) is required at screening and when clinically indicated. ECGs for each participant should be obtained from the same machine wherever possible. Lead placement should be as consistent as possible. ECG recordings must be performed after the participant has been resting in a supine position for at least 10 minutes.

For safety monitoring purposes, the investigator must review, sign, and date all ECG reports. Paper copies of ECG tracings will be kept as part of the participant's permanent study file at the site. Any morphologic waveform changes or other ECG abnormalities must be documented on the eCRF.

4.5.8 Clinical Outcome Assessments

Participant-reported outcome (PRO) instruments and HCP questionnaires (HCPQ) will be completed to characterize the clinical profile of atezolizumab infusions and injections. In addition, these instruments will enable the capture of the participant's and HCP's direct experience with atezolizumab infusions and injections.

PRO data will be collected through use of the following instruments: Patient Preference Questionnaire (PPQ), Therapy Administration Satisfaction Questionnaires (SC and IV versions; TASQ-SC and TASQ-IV), EORTC QLQ-C30, and EQ-5D-5L. HCP data will be collected through the use of the HCPQs (treatment room and drug preparation area versions). PRO and HCPQ data will be collected on paper questionnaires.

4.5.8.1 Data Collection Methods for Clinical Outcome Assessments

PRO and HCP instruments will be self-administered at the clinic at specified timepoints during the study (see schedule of activities in [Appendix 1](#)). At the clinic, the EORTC QLQ-C30 and EQ-5D-5L will be administered before the participant receives any information on disease status, and prior to the performance of non-PRO assessments. The PPQ and TASQ will be administered following treatment administration per the schedule of activities.

PRO instruments, translated into the local language as appropriate, will be provided by the Sponsor.

During clinic visits, PRO instruments should be administered as outlined below:

- Participants' health status should not be discussed prior to administration of the instruments.
- Sites must administer the official version of each instrument, as provided by the Sponsor. Instruments must not be copied from the protocol.
- Sites should allow sufficient time for participants to complete the instruments, estimated to be 13 minutes at the Cycle 1 Day 1 and Cycle 3 Day 1 visits, 15 minutes at the Cycle 6 Day 1 visit, and 8 minutes at the Treatment Continuation, end-of-treatment, and follow-up visits.
- Sites should administer the instruments in a quiet area with minimal distractions and disruptions.
- Participants should be instructed to answer questions to the best of their ability; there are no right or wrong answers.
- Site staff should not interpret or explain questions, but may read questions verbatim upon request.
- Participants should not obtain advice or help from others (e.g., family members or friends) when completing the instruments.
- Site staff should review all completed instruments and should ask the participant to rectify any response that is not clearly marked in the appropriate location. If a response is missing, site staff should ask the participant to complete the item or confirm that the item was intentionally left blank.

4.5.8.2 Description of Clinical Outcome Assessment Instruments *Patient Preference Questionnaire*

The PPQ is a generic preference questionnaire designed to ask patients about which route of administration they preferred after receiving both the SC and IV formulations. Question 1 asks patients to report their preference for the route of administration (IV, SC, or no preference). Question 2 asks patients to rate the strength of their preference (if any) on a 3-point scale (very strong, fairly strong, not very strong). Question 3 asks patients to provide two main reasons for their preference (see [Appendix 4](#)).

The PPQ will be completed immediately after 3 cycles of each treatment (i.e., Day 1 of Cycle 6 of the Treatment Crossover Period) to allow participants to have experience with both routes of administration and to determine if additional treatment by one route or another modified their preference. Please refer to [Appendix 1](#) for instructions regarding when participants who prematurely discontinue study treatment should complete the PPQ.

Therapy Administration Satisfaction Questionnaires

Participant-reported treatment satisfaction with atezolizumab IV and atezolizumab SC will be evaluated using the TASQ-IV and TASQ-SC, respectively (see [Appendix 4](#)).

Each TASQ will be completed by the participant as outlined in the schedule of activities (see [Appendix 1](#)).

EORTC QLQ-C30

The QLQ-C30 is a validated, reliable self-report measure (Aaronson et al. 1993; Fitzsimmons et al. 1999) (see [Appendix 4](#)). It consists of 30 questions that assess five aspects of participant functioning (physical, emotional, role, cognitive, and social), three symptom scales (fatigue, nausea and vomiting, and pain), global health status and quality of life (QoL), and six single items (dyspnea, insomnia, appetite loss, constipation, diarrhea, and financial difficulties) with a recall period of the previous week. Scale scores can be obtained for the multi-item scales. The functioning and symptoms items are scored on a four-point scale that ranges from "not at all" to "very much", and the global health status and QoL items are scored on a seven-point scale that ranges from "very poor" to "excellent". The QLQ-C30 takes approximately 10 minutes to complete. The QLQ-C30 will be completed by the participant as outlined in the schedule of activities (see [Appendix 1](#)).

Healthcare Professional Questionnaires

Healthcare professional reported perception of time and resource use associated with atezolizumab SC will be assessed via two HCPQs (see [Appendix 5](#)). One HCPQ (HCPQ-Treatment Room) will be completed by an HCP involved in treatment preparation and/or administration in the treatment room where study drugs are administered. The other HCPQ (HCPQ-Drug Preparation Area) will be completed by an HCP involved in study drug preparation. Please refer to each HCPQ in [Appendix 5](#) for

personnel qualifying as HCPs for each questionnaire. The HCPQs will be completed by the HCP as outlined in the schedule of activities (see [Appendix 1](#)).

EuroQol EQ-5D-5L

The EQ-5D-5L is a validated self-report health status questionnaire that is used to calculate a health status utility score for use in health economic analyses (EuroQol Group 1990; Brooks 1996; Herdman et al. 2011; Janssen et al. 2013) (see [Appendix 6](#)). There are two components to the EQ-5D-5L: a five-item health state profile that assesses mobility, self-care, usual activities, pain/discomfort, and anxiety/depression, as well as a visual analog scale (VAS) that measures health state. The EQ-5D-5L is designed to capture the participant's current health status. Published weighting systems allow for creation of a single composite score of the participant's health status. The EQ-5D-5L takes approximately 3 minutes to complete. It will be used in this study for informing pharmacoeconomic evaluations. The EQ-5D-5L will be completed by the participant as outlined in the schedule of activities (see [Appendix 1](#)).

4.6 TREATMENT, PARTICIPANT, STUDY, AND SITE DISCONTINUATION

4.6.1 Study Treatment Discontinuation

Participants must permanently discontinue study treatment (atezolizumab) if any of the following criteria are met:

- Intolerable toxicity related to study treatment, including development of an immune-mediated adverse event determined by the investigator to be unacceptable given the individual participant's potential response to therapy and severity of the event
- Any medical condition that may jeopardize the participant's safety if he or she continues study treatment
- Investigator or Sponsor determination that treatment discontinuation is in the best interest of the participant
- Use of another non-protocol anti-cancer therapy
- Pregnancy
- Loss of clinical benefit as determined by the investigator after an integrated assessment of radiographic and biochemical data, local biopsy results (if available), and clinical status (e.g., symptomatic deterioration such as pain secondary to disease) (see [Section 3.1.1](#))

The primary reason for study treatment discontinuation should be documented on the appropriate eCRF. Participants who discontinue atezolizumab prematurely during the study treatment period will not be replaced.

Patients will return to the clinic for a treatment discontinuation visit ≤ 30 days after the final dose of study treatment. An earlier visit may be used as the treatment discontinuation visit if a local assessment of tumor response indicates a loss of clinical benefit.

Refer to the schedule of activities (see [Appendix 1](#)) for details on follow-up assessments to be performed for participants who permanently discontinue atezolizumab. If a participant requests to be withdrawn from treatment or follow-up assessments, this request must be documented in the source documents and signed by the investigator.

4.6.2 Participant Discontinuation from the Study

Participants have the right to voluntarily withdraw from the study at any time for any reason. In addition, the investigator has the right to withdraw a participant from the study at any time.

Reasons for participant discontinuation from the study may include, but are not limited to, the following:

- Participant withdrawal of consent
- Study termination or site closure
- Adverse event
- Loss to follow-up
- Participant non-compliance, defined as failure to comply with protocol requirements as determined by the investigator or Sponsor

Every effort should be made to obtain a reason for participant discontinuation from the study. The primary reason for discontinuation from the study should be documented on the appropriate eCRF. If a participant requests to be withdrawn from the study, this request must be documented in the source documents and signed by the investigator. Participants who withdraw from the study will not be replaced.

4.6.3 Study Discontinuation

The Sponsor has the right to terminate this study at any time. Reasons for terminating the study may include, but are not limited to, the following:

- The incidence or severity of adverse events in this or other studies indicates a potential health hazard to participants
- Participant enrollment is unsatisfactory
- Development of atezolizumab SC formulation is discontinued

The Sponsor will notify the investigator if the Sponsor decides to discontinue the study.

4.6.4 Site Discontinuation

The Sponsor has the right to close a site at any time. Reasons for closing a site may include, but are not limited to, the following:

- Excessively slow recruitment
- Poor protocol adherence
- Inaccurate or incomplete data recording
- Non-compliance with the International Council for Harmonisation (ICH) guideline for Good Clinical Practice
- No study activity (i.e., all participants have completed the study and all obligations have been fulfilled)

5. ASSESSMENT OF SAFETY

5.1 SAFETY PLAN

The safety plan for participants in this study is based on clinical experience with atezolizumab and rHuPH20 in completed and ongoing studies. The anticipated important safety risks are outlined below in Sections 5.1.1 and 5.1.2).

Measures will be taken to ensure the safety of participants in this study, including the use of stringent inclusion and exclusion criteria and close monitoring of participants during the study. Administration of atezolizumab will be performed in a monitored setting in which there is immediate access to trained personnel and adequate equipment and medicine to manage potentially serious reactions. Guidelines for managing participants who experience anticipated adverse events, including criteria for treatment interruption or discontinuation, are provided in [Appendix 9](#). Refer to Sections 5.2–5.7 for details on safety reporting (e.g., adverse events, pregnancies) for this study.

Participants with active infection are excluded from study participation. In the setting of a pandemic or epidemic, screening for active infections (including SARS-CoV-2) prior to and during study participation should be considered according to local or institutional guidelines or guidelines of applicable professional societies (e.g., American Society of Clinical Oncology or European Society for Medical Oncology).

Severe SARS-CoV-2 infection appears to be associated with a CRS involving the inflammatory cytokines IL-6, IL-10, IL-2, and IFN- γ (Merad and Martin 2020). If a participant develops suspected CRS during the study, a differential diagnosis should include SARS-CoV-2 infection, which should be confirmed or refuted through assessment of exposure history, appropriate laboratory testing, and clinical or radiologic evaluations per investigator judgment. If a diagnosis of SARS-CoV-2 infection is confirmed, the disease should be managed as per local or institutional guidelines.

5.1.1 Risks Associated with Atezolizumab

Atezolizumab has been associated with risks such as the following: infusion-related reaction (IRRs) and immune-mediated hepatitis, pneumonitis, colitis, pancreatitis, diabetes mellitus, hypothyroidism, hyperthyroidism, adrenal insufficiency, hypophysitis, Guillain-Barré syndrome, myasthenic syndrome or myasthenia gravis, facial palsy, myelitis, meningoencephalitis, myocarditis, pericardial disorders, nephritis, myositis, and severe cutaneous adverse reactions. In addition, immune-mediated reactions may involve any organ system and lead to hemophagocytic lymphohistiocytosis (HLH). Refer to [Appendix 9](#) of the protocol and Section 6 of the atezolizumab Investigator's Brochure for a detailed description of anticipated safety risks for atezolizumab.

Guidelines for managing participants who experience anticipated adverse events are provided in [Appendix 9](#).

5.1.2 Risks Associated with rHuPH20

rHuPH20 is co-formulated with atezolizumab. rHuPH20 should not be injected into or around an infected or acutely inflamed area because of the danger of spreading a localized infection. Refer to the rHuPH20 U.S. Package Insert for more details regarding the full safety profile of rHuPH20, including boxed warnings and contraindications (Hylenex recombinant U.S. Package Insert). Refer to [Appendix 9](#) for adverse event management guidelines for atezolizumab.

5.2 SAFETY PARAMETERS AND DEFINITIONS

Safety assessments will consist of monitoring and recording adverse events, including serious adverse events and adverse events of special interest, performing protocol-specified safety laboratory assessments, measuring protocol-specified vital signs, and conducting other protocol-specified tests that are deemed critical to the safety evaluation of the study.

Certain types of events require immediate reporting to the Sponsor, as outlined in Section [5.4](#).

5.2.1 Adverse Events

According to the ICH guideline for Good Clinical Practice, an adverse event is any untoward medical occurrence in a clinical investigation subject administered a pharmaceutical product, regardless of causal attribution. An adverse event can therefore be any of the following:

- Any unfavorable and unintended sign (including an abnormal laboratory finding), symptom, or disease temporally associated with the use of a medicinal product, whether or not considered related to the medicinal product
- Any new disease or exacerbation of an existing disease (a worsening in the character, frequency, or severity of a known condition) (see Sections [5.3.5.9](#) and [5.3.5.10](#) for more information)

- Recurrence of an intermittent medical condition (e.g., headache) not present at baseline
- Any deterioration in a laboratory value or other clinical test (e.g., ECG, X-ray) that is associated with symptoms or leads to a change in study treatment or concomitant treatment or discontinuation from study treatment
- Adverse events that are related to a protocol-mandated intervention, including those that occur prior to assignment of study treatment (e.g., screening invasive procedures such as biopsies)

5.2.2 Serious Adverse Events (Immediately Reportable to the Sponsor)

A serious adverse event is any adverse event that meets any of the following criteria:

- Is fatal (i.e., the adverse event actually causes or leads to death)
- Is life threatening (i.e., the adverse event, in the view of the investigator, places the participant at immediate risk of death)
 - This does not include any adverse event that, had it occurred in a more severe form or was allowed to continue, might have caused death.
- Requires or prolongs inpatient hospitalization (see Section 5.3.5.11)
- Results in persistent or significant disability/incapacity (i.e., the adverse event results in substantial disruption of the participant's ability to conduct normal life functions)
- Is a congenital anomaly/birth defect in a neonate/infant born to a mother exposed to study treatment
- Is a significant medical event in the investigator's judgment (e.g., may jeopardize the participant or may require medical/surgical intervention to prevent one of the outcomes listed above)

The terms "severe" and "serious" are not synonymous. Severity refers to the intensity of an adverse event (e.g., rated as mild, moderate, or severe, or according to NCI CTCAE; see Section 5.3.3); the event itself may be of relatively minor medical significance (such as severe headache without any further findings).

Severity and seriousness need to be independently assessed for each adverse event recorded on the eCRF.

Serious adverse events are required to be reported by the investigator to the Sponsor immediately (i.e., no more than 24 hours after learning of the event; see Section 5.4.2 for reporting instructions).

5.2.3 Adverse Events of Special Interest (Immediately Reportable to the Sponsor)

Adverse events of special interest are required to be reported by the investigator to the Sponsor immediately (i.e., no more than 24 hours after learning of the event; see Section 5.4.2 for reporting instructions). Adverse events of special interest for this study are as follows:

- Cases of potential drug-induced liver injury that include an elevated ALT or AST in combination with either an elevated bilirubin or clinical jaundice, as defined by Hy's Law (see Section 5.3.5.7)
- Suspected transmission of an infectious agent by a study treatment, as defined below:

Any organism, virus, or infectious particle (e.g., prion protein transmitting transmissible spongiform encephalopathy), pathogenic or non-pathogenic, is considered an infectious agent. A transmission of an infectious agent may be suspected from clinical symptoms or laboratory findings that indicate an infection in an individual exposed to a medicinal product. This term applies only when a contamination of the study treatment is suspected.
- Systemic lupus erythematosus
- Events suggestive of hypersensitivity, infusion-related reactions, cytokine release syndrome, HLH, and MAS
- Nephritis
- Ocular toxicities (e.g., uveitis, retinitis, optic neuritis)
- Grade ≥ 2 cardiac disorders
- Vasculitis
- Autoimmune hemolytic anemia
- Severe cutaneous reactions (e.g., Stevens-Johnson syndrome, dermatitis bullous, toxic epidermal necrolysis)
- Myelitis
- Facial paresis

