5.2.4 Selected Adverse Events **Injection-Site Reactions**

With SC administration, local reactions at site of injection (erythema, pruritus, edema, rash, and pain) may occur. In case of severe injection-site reactions, unscheduled photographs will be taken. Photographs should include a label showing the subject's identification number and initials, date and time of calendar date, and a centimeter ruler to provide scale. Efforts will be made to standardize the photography with regard to parameters such as angle, light, distance from body, and settings.

See Section 5.3.5.1 for instructions on reporting injection-related reactions and infusion-related reactions.

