5.3.5.1 Infusion-Related Reactions, Injection-Related Reactions, and Cytokine Release Syndrome

There may be significant overlap in signs and symptoms of infusion-related reactions/injection-related reactions and cytokine release syndrome (CRS). While infusion-related reactions/injection-related reactions occur during or within 24 hours after treatment administration, time to onset of CRS may vary. Differential diagnosis should be applied, particularly for late-onset CRS (occurring more than 24 hours after treatment administration), to rule out other etiologies such as delayed hypersensitivity reactions, sepsis or infections, HLH, tumor lysis syndrome, early disease progression, or other manifestations of systemic inflammation.

Adverse events that occur during or within 24 hours after study treatment administration and are judged to be related to study treatment infusion or injection should be captured on the Adverse Event eCRF as a diagnosis (e.g., "infusion-related reaction", "injection-related reaction", or "cytokine release syndrome"). Avoid ambiguous terms such as "systemic reaction". Cases of late-onset CRS should be reported as "cytokine-release syndrome" on the Adverse Event eCRF. Associated signs and symptoms of an infusion-related reaction/injection-related reaction should be recorded on the dedicated Infusion-Related Reaction and Injection-Related Reaction eCRF.

If a participant experiences both a local and systemic reaction to a single administration of study treatment, each reaction should be recorded as a separate event on the Adverse Event eCRF, with associated signs and symptoms of an infusion-related reaction/injection-related reaction also recorded separately on the dedicated Infusion-Related Reaction or Injection-Related Reaction eCRF.

In recognition of the challenges in clinically distinguishing between these two events, consolidated guidelines for medical management of infusion-related reactions/injection-related reactions and CRS are provided in [Appendix 9](#).

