4.3.2 Adverse Events

After informed consent has been obtained but prior to initiation of study treatment, only serious adverse events caused by a protocol-mandated intervention (e.g., invasive procedures such as biopsies, discontinuation of medications) should be reported.

After initiation of study treatment, all adverse events will be reported until 30 days after the final dose of study treatment or until initiation of new systemic anti-cancer therapy, whichever occurs first, and serious adverse events and adverse events of special interest will continue to be reported until 90 days after the final dose of study treatment or until initiation of new systemic anti-cancer therapy, whichever occurs first.

After the end of the reporting period for serious adverse events and adverse events of special interest (defined as 90 days after the final dose of study treatment or until initiation of new systemic anti-cancer therapy, whichever occurs first), all deaths, regardless of cause, should be reported through use of the Long-Term Survival Follow-Up eCRF.

All verbatim adverse event terms will be mapped to Medical Dictionary for Regulatory Activities thesaurus terms, and adverse event severity will be graded according to NCI CTCAE v5.0. All adverse events, serious adverse events, adverse events leading to death, adverse events of special interest, and adverse events leading to study treatment discontinuation that occur on or after the first dose of study treatment (i.e., treatment-emergent adverse events) will be summarized by mapped term, appropriate thesaurus level, and severity grade. For events of varying severity, the highest grade will be used in the summaries. Deaths and cause of death will be summarized.

To evaluate the safety of switching from atezolizumab SC to atezolizumab IV and from atezolizumab IV to atezolizumab SC, adverse event summaries will also be produced for the Treatment Cross-over Period by treatment arm and treatment period, as well as potentially by cycle. In addition, summaries of AE rate adjusted for patient-years at risk may be produced by treatment arm and treatment period.

An adverse event will be allocated to the treatment received on or before the adverse event start date.

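### The AESI list names infusion-related but not injection-related reactions, so AESI counts and 24-hour reporting of some non-serious systemic reactions may differ by route

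*Protocol*

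**What the plan says.** Protocol Section 5.2.3 lists the events that must reach the Sponsor within 24 hours as AESIs. One item reads "Events suggestive of hypersensitivity, infusion-related reactions, cytokine release syndrome, HLH, and MAS". It does not mention injection-related reactions, and nothing in the section says that the infusion term covers both routes.

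Protocol Section 5.3.5.1 sets the recording rule. Events that start during dosing or within 24 hours after it, and that are "judged to be related to study treatment infusion or injection should be captured on the Adverse Event eCRF as a diagnosis", are entered under a diagnosis term. The examples given are infusion-related reaction, injection-related reaction and CRS. The same section keeps local and systemic reactions apart: when one dose causes both, each gets its own entry on that form.

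Protocol Section 5.2.4, directly after the AESI list, deals with local reactions at the SC injection site and then points elsewhere: "See Section 5.3.5.1 for instructions on reporting injection-related reactions and infusion-related reactions".

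SAP Section 4.3.2 lists what will be summarised: "All adverse events, serious adverse events, adverse events leading to death, adverse events of special interest, and adverse events leading to study treatment discontinuation". For the safety of switching it adds that "adverse event summaries will also be produced for the Treatment Cross-over Period by treatment arm and treatment period".

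**The concern.** The safety objectives in Protocol Section 2.3 concern SC, IV and the switch between them, so an event category that is compared across routes should be defined in the same way on both. Here the recording terms depend on the route, and only the IV term is on the AESI list. An IV reaction qualifies by its name alone. An SC reaction recorded as injection-related qualifies only if it also suggests one of the other listed conditions, which asks for an additional judgement on one route only, in an open-label study.

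Two things are at stake. The first is the AESI summary: in the cross-over period, arm and period together identify the route, so a difference in definition could look like a difference in safety. The second is oversight: under Protocol Section 5.7 the Sponsor promptly evaluates serious adverse events and AESIs against cumulative product experience, and an unlisted, non-serious reaction is outside that process. SAP Section 1.2.3 provides for no data monitoring that would act as a second check.

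**Working it through.** No figure in the plan bears on this point, so the check is to set the passages side by side.

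**1. Are the two terms really distinct in the protocol?** Section 5.3.5.1 pairs them in its heading and text and gives them as separate diagnoses. In Section 4.3.2, Table 1 (SC) speaks of injection-related reactions and Table 2 (IV) of infusion-related reactions. The terms are used as route-specific.

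**2. Does any other passage bring injection-related reactions into the AESI list?** Section 5.2.4 covers local reactions and refers onward for recording; it gives no AESI status. SAP Section 4.3.2 contains no AESI term list, and SAP Section 5 states that there is no supporting document. Protocol Section 3.3.4 mentions infusion-related reactions with either route of administration. That is a route-neutral use of the term, at odds with Section 5.3.5.1, and it adds ambiguity without settling it.

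**3. Which reactions are affected?** For a systemic reaction within 24 hours of a dose:

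| Reaction | After IV | After SC |
|---|---|---|
| Suggestive of hypersensitivity, CRS, HLH or MAS | AESI | AESI |
| Serious | Reported within 24 hours and in the SAE tables | Reported within 24 hours and in the SAE tables |
| Non-serious, suggestive of none of these conditions, recorded under the route's own term | AESI, as an infusion-related reaction | Not a named AESI |

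Only the last row treats the routes differently for both the AESI count and prompt reporting. Local injection-site reactions are a separate matter under Section 5.2.4.

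**4. Which direction, and how large?** Suppose the risk *r* of a systemic administration reaction is the same on both routes, with *N* participants exposed to each. Suppose also that every IV case is an AESI, and that a share *h* of SC cases qualifies through hypersensitivity, CRS, HLH or MAS. The expected AESI counts from these reactions are:

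- IV: *N* × *r*
- SC: *N* × *r* × *h*
- Ratio SC to IV: *h*

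Since *h* lies between 0 and 1, SC can show as many AESIs as IV or fewer, but not more. At *h* = 1 there is no difference. The documents supply neither *r* nor *h*, so the direction follows from the wording but the size does not.

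**The case against.** The strongest reply is that the AESI item already covers the reactions that matter. It is worded around events that suggest certain conditions; hypersensitivity, CRS, HLH and MAS carry no route limit; and Section 5.3.5.1 itself notes that injection-related reactions and CRS overlap in presentation. A reader might infer that the same systemic reaction is always an AESI on IV and never on SC. The documents do not support that: it would need *h* = 0, against the plain wording of the item. This part of the reply stands, and it limits the point to the remaining SC reactions.

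A second reply is that infusion-related reaction is meant as shorthand for both routes. Section 3.3.4 leans that way. So does Appendix 9, where the management row is labelled only for infusion-related reactions and CRS although Section 5.3.5.1 says that the guidance there covers injection-related reactions too. This may well be the intention. It is not stated, however, and the recording rule points sites the other way.

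A third reply is that the comparison of routes does not need AESI status. Every reaction goes on the Adverse Event eCRF, its signs and symptoms go on a dedicated form, and all adverse events are summarised by mapped term and grade. A reader of the report can compare infusion- and injection-related reactions directly. This also stands. In addition, SAP Section 4.3.2 promises adverse event summaries by arm and period without expressly promising AESI tables at that level, and it specifies no test.

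Two further inferences should be resisted. One is that the longer AESI reporting window matters here. These reactions begin within 24 hours of a dose, and under Section 5.3.1 all adverse events are collected for 30 days after the final dose unless new systemic anti-cancer therapy starts first, so the 90-day window adds almost nothing to their capture. The other is a numerical gap between routes. Any such number would rest on an assumed reaction rate and an assumed share of SC cases missed.

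**Conclusion.** The point holds in a limited form and is worth a cheap improvement. As written, a non-serious systemic SC reaction that is recorded only as injection-related, and is not judged suggestive of hypersensitivity, CRS, HLH or MAS, is not a named AESI, while its IV counterpart is. AESI counts and 24-hour reporting may therefore differ by route, in the direction of fewer AESIs on SC.

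This rests on sites using the route-specific terms as Section 5.3.5.1 sets out, and on the AESI list being read literally. If sites read the infusion term as covering both routes, or judge every SC reaction to fall under one of the other conditions, the difference disappears. The size cannot be derived from the documents. Overall adverse event and SAE tables are unaffected, serious reactions are reported within 24 hours on both routes, and the primary preference endpoint is not touched.

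**What to change.** In Protocol Section 5.2.3, replace *infusion-related reactions* with *infusion-related reactions and systemic injection-related reactions*. Leave local injection-site reactions where they are, under Section 5.2.4.

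In SAP Section 4.3.2, tabulate the two terms together as one AESI group. The existing rule, which allocates an event to the treatment received on or before its start date, already assigns each case to a route and needs no change. Name the terms that enter the group, so that local injection-site events are left out of it.

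The SAP grouping can be built from what sites already record, because local and systemic reactions are separate entries with their signs and symptoms on a dedicated form. It can be applied to reactions already on file. The change to 24-hour reporting works only from the amendment onwards. The downside is a few more expedited reports of non-serious reactions.
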